## **13) Provisions to Monitor the Data to Ensure the Safety of Subjects\***

The PI and all key personnel involved in this study have completed the Collaborative IRB Training Initiative (CITI), a mandatory tutorial on the responsible conduct of human subject research. The tutorial and institutional policies and procedures governing the conduct of human subjects research are available on the UMass Medical School intranet website and may be accessed by the Investigator and key study personnel if questions arise.

The PI will immediately report to the IRB any unanticipated problems or adverse events that occur during the conduct of the study, after study completion, or after subject withdrawal in accordance with adverse event and unanticipated problems reporting guidelines.

Safety monitoring will have two components. The first will focus on change in psychiatric symptoms. Safety monitoring will also assess the incidence and severity of side effects and the frequency and reason for any medication changes and study medication discontinuation. The PI will discuss likely side effects of exenatide and potential risks of study procedures as part of the informed consent procedure.

Investigators and research personnel who are trained and experienced at conducting assessments in persons with schizophrenia, will assess for deteriorating mental status and/or suicidal ideation. Participants will meet with a study psychiatrist at each visit and have routine monitoring of psychiatric symptoms. The PI will be notified immediately if subject expresses suicidal ideation. The PI is a board certified psychiatrist and has the necessary training and experience to address such events.

The PI can be contacted by phone at all times and the UMass Memorial Emergency Service is available for psychiatric and medical assessment of research subjects. Female patients will be screened for pregnancy during enrollment by a urine pregnancy test.

Any adverse effect reported to study personnel will be reviewed with the PI who will determine whether they are mild, moderate or serious. Potentially serious adverse events will be reviewed by an external monitoring team to determine the likelihood (unlikely/possible/probable) that it is related to the study medication and whether it is safe for the subject to remain in the study.

Continuous data and safety monitoring will be conducted by the PI. The monitoring will include all adverse events (AEs and SAEs) both expected and unexpected, enrollment, dropout rates and protocol deviations in addition to the results of special studies and laboratory tests that are conducted to ensure patient safety, subject interview and conduct, review of subject symptom or performance status, review of clinical test results, review of subject physical examination, review of all vital signs, diagnostic tests, and evaluations. The investigator will report adverse events to the IRB in accordance with IRB guidelines.

The PI will create a Data Safety Monitoring Board (DSMB) to independently oversee this clinical trial. The DSMB for this study will be composed of at least three people and will include a psychiatrist, an endocrinologist and a biostatistician who will be independent of the study group. The group will follow the NIH policy for data and safety monitoring and guidelines as published on <http://www.nimh.nih.gov/research-funding/grants/nimh-policy-on-data-and-safety-monitoring-in-extramural-investigator-initiated-clinical-trials.shtml>. Study data regarding subject enrollment, characteristics, symptoms, adverse events and serious adverse events will be submitted to the DSMB for review and analysis annually. The DSMB will review study data, the safety of study participants and conduct of the study. It will advise the PI on continuation of the study and provide reports to the IRB regarding recruitment of appropriate subjects and presence of adverse effects.

An explicit stopping rule will be followed for a potentially serious psychiatric decompensation in order to further enhance patient safety: active subjects will be terminated from the study if they experience an increase in PANSS total score greater than or equal to 20 compared to their baseline score at any point during the study.

Subjects will be terminated from the study if their eGFR falls below 30 ml/min at any point during the study.

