### Safety Endpoints:

An EKG will be conducted at the beginning and end of the study to assess safety. Vital Signs including blood pressure will be collected at every visit. Data on adverse events will be collected at every visit using the side effects questionnaires (SEQ and SEQabbrev) to assess safety and tolerability.

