#### **14) Withdrawal of Subjects\***

Subjects will be withdrawn from the study if they are determined to meet ineligibility criteria after enrollment. If subjects have laboratory results that meet the exclusionary criteria range during the study, the subject will have his/her labs repeated before being withdrawn from the study.

The study medication will be stopped if a subject has a serious adverse event, but will not necessarily be stopped for exacerbation of psychiatric symptoms or any other adverse event. If the PI or co-investigator considers continuation of the study medication to be safe after a worsening of psychiatric symptoms, and the subject wishes to continue, the subject's treating psychiatrist will be contacted and will make the final decision whether the subject will be allowed to continue taking study medication.

Female subjects may be terminated from the study if they become pregnant at any time while participating in the study. Subjects who fail the urine screening for illegal drugs during the screening visit will be deemed a screen fail and terminated from the study. We will not document the results from the urine drug screen in the patient study records. We will maintain a separate log of the reasons for screen fail. This log will have the counts of screen fails for various exclusion factors including current substance abuse. This log will have no subject information and will have no link to subject id.

Subjects may also withdraw their consent from the study at any time for any reason, including: physical or emotional discomfort associated with taking the study medication, physical or emotional discomfort associated with performing study procedures, or inability to come in for required study visits.

If at any time the study sponsor or research personnel at UMass decide to terminate the study, subjects' consent will be withdrawn involuntarily.

For subjects terminated or withdrawn from the study, they will be asked to have an "exit" visit. Vital signs, ECG, side effect assessment and routine blood tests (CBC, basic metabolic profile) will be performed during the visit.

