## **22) Resources Available**

All research personnel have completed CITI training and are aware of Good Clinical Practices (GCP). The PI is a senior psychiatrist who specializes in schizophrenia treatment and research. Both the Principal Investigator and Co-Investigator each have more than 10 years of experience working with individuals suffering from schizophrenia and substance abuse.

The study coordinator (i.e. research assistant) will be involved in activities such as reviewing study procedures with each subject, obtaining informed consent, data-entry, and blood sample collection. The study coordinator will also be responsible for administering questionnaires and conducting assessments. The study coordinator is certified in phlebotomy, and has completed sufficient training in order to obtain informed consent, conduct study assessments, enter data, etc.

The PI will be held responsible for oversight of the study procedure. The PI and Co-Investigator will also be responsible for identifying AEs and SAEs and for terminating a subject if their physical and/or mental health is compromised as a result of the study treatment.

Research nurses who are qualified registered nurses (RN) may be involved in study activities such as administering Exenatide injections and completing questionnaires and other study assessments.

The PI will discuss individual roles with each member of the research team once the study commences.

The PI can be contacted by phone and the UMass Memorial Emergency Service is available for psychiatric and medical assessment of research subjects.

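### The protocol's only adverse-event grade has no severe level and ends in a seriousness term, so it cannot record both intensity and seriousness

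*Protocol*

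**What the plan says.** Protocol section 13 commits to measuring severity: "Safety monitoring will also assess the incidence and severity of side effects". The same section then gives the one grading instruction found in either document: "Any adverse effect reported to study personnel will be reviewed with the PI who will determine whether they are mild, moderate or serious".

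Elsewhere the protocol treats seriousness as a class of event. Section 13 lists AEs and SAEs separately, both for the investigator's continuous monitoring and for the data sent to the DSMB. Section 22 assigns the task: "The PI and Co-Investigator will also be responsible for identifying AEs and SAEs". Section 14 attaches an action to the class: "The study medication will be stopped if a subject has a serious adverse event", whereas the drug "will not necessarily be stopped for exacerbation of psychiatric symptoms or any other adverse event". Section 13 also provides that "Potentially serious adverse events will be reviewed by an external monitoring team", which judges relatedness and whether the subject may safely continue.

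Neither document defines an SAE or says whether the three-level grade serves as the SAE flag. Section 9 names two side-effect questionnaires (SEQ and SEQabbrev) as the collection tool but does not describe their items. The SAP says only that side effects were assessed weekly, and its statistical analysis section does not mention adverse events.

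**The concern.** Severity and seriousness are different attributes. Severity is how intense an event is. Seriousness is whether it belongs to a class, usually set by outcome, that triggers reporting and action. The grade starts on the first scale and ends on the second.

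Take intense nausea that does not lead to hospitalisation, and suppose that seriousness is defined by outcomes such as hospitalisation (an assumption, since the protocol gives no definition). If the top level means SAE, the investigator has to call this event moderate, which understates it, or serious, which misclassifies it. The example is realistic for this drug: section 15 lists nausea, vomiting, diarrhea, constipation and headache among the common effects, and any of these can be intense without being serious.

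At stake is whether the trial can report tolerability as section 13 promises. A table of this grade by arm could not be read without knowing what the top level meant. A smaller matter is that the top level shares its key word with the mandatory drug stop in section 14.

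**Working it through.** The plan states no figure to reproduce. The check sets the classifications side by side and then tests what the grade can hold.

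**Step 1. Does another scale fill the gap?** The documents contain three other ways of sorting events:
- Relatedness (unlikely, possible, probable), section 13: this is causality, and it covers potentially serious events only.
- Common, less common, rare, section 15: this is the expected frequency of known side effects.
- AE versus SAE, sections 13, 14 and 22: this is an event class, with no criteria given.

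None of them is an intensity scale, so the grade in section 13 is the only stated place for severity.

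**Step 2. What can the grade hold?** Three intensities (mild, moderate, severe) crossed with two classes (non-serious, serious) give 3 × 2 = 6 combinations. The grade has three labels.

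| Intensity | Serious? | Top level means SAE | Top level means severe |
|---|---|---|---|
| Mild | No | Both recorded | Intensity only |
| Moderate | No | Both recorded | Intensity only |
| Severe | No | No correct level | Intensity only |
| Mild | Yes | Seriousness only | Intensity only |
| Moderate | Yes | Seriousness only | Intensity only |
| Severe | Yes | Seriousness only | Intensity only |

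- Top level means SAE: intensity is recorded in 2 of 6, seriousness in 2 + 3 = 5 of 6, and both in 2 of 6.
- Top level means severe: intensity is recorded in 6 of 6, seriousness in 0 of 6, and both in 0 of 6.
- Two separate fields: both are recorded in 6 of 6.

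The conclusion therefore does not depend on which meaning was intended. What is lost does: under the first meaning it is mostly intensity, and under the second it is SAE status, which the protocol says is identified elsewhere.

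**Step 3. Does the drug stop depend on the grade?** Section 14 acts on a serious adverse event. Section 22 makes identifying SAEs a duty of the PI and Co-Investigator, and no sentence says they do it by means of the grade. If SAEs are identified separately, the stop rule never reads the grade, and there are 0 of 6 combinations in which the grade could change the decision.

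**The case against.** The strongest reply is that seriousness is already looked after. SAEs are monitored and sent to the DSMB as their own category, identified by named people, and backed by external review. That review starts from events that are only potentially serious, a wider net than the top level of the grade, and it decides whether the subject may safely stay in the study. Section 22 also makes the investigators responsible for terminating a subject harmed by the treatment. All of this stands, and it limits the point to the recording of severity.

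A reader might infer more: that the grade would cause the drug to be stopped wrongly, or leave it running after an SAE. The documents do not support that. It would require the grade to be used as the SAE flag, which is nowhere stated. The worst case would also require the PI, who both grades events and helps identify SAEs, to mean severe when grading and SAE when applying the stop rule to the same event.

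A reader might also point to this sentence in section 13: "An explicit stopping rule will be followed for a potentially serious psychiatric decompensation". Because it is tied to a PANSS rise of 20 or more, it could be taken to show that serious means severe in this protocol. It fits risk of a serious event equally well, so nothing here rests on it.

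Finally, the questionnaires or the case-report form may have their own severity item. That is possible and cannot be settled from the documents. If they do, the data exist and only the protocol wording needs repair.

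**Conclusion.** The point holds as a minor issue of safety recording. Section 13 promises severity and then gives a grade that cannot deliver both severity and seriousness under either meaning of its top level: 2 of 6 combinations are fully recorded under one meaning and 0 of 6 under the other, against 6 of 6 with two fields. These are counts of categories, unweighted by how often each occurs. The number of subjects affected cannot be derived from the documents.

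The main effect is incomplete or ambiguous severity data. The word shared with the drug-stop rule is a secondary risk that arises only if staff treat the grade as the SAE flag. The wording defect is certain. Whether any severity data were actually lost depends on forms that are not in the documents. Nothing here bears on the efficacy analysis, the DSMB's access to SAEs or the renal stopping criterion.

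**What to change.** - **Section 13:** grade intensity as mild, moderate or severe. Record seriousness as a separate yes/no item against an SAE definition written into the protocol. The protocol cites IRB reporting guidelines and an NIH monitoring policy, but neither document sets out or cites an SAE definition. Keep external review for potentially serious events.
- **Section 14:** state that the mandatory drug stop follows the seriousness item. Severe non-serious events stay a matter of judgement, as they are now.
- **Reporting:** summarise each attribute by arm with one value per subject, namely worst severity and any SAE. Side effects are assessed weekly, so one subject can contribute several events, and a test on event counts would treat them as independent. The SAP should state this summary explicitly, because its analysis section does not address adverse events.

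The SAP is dated 11/30/2019 and written in the past tense. If data collection has ended, state which meaning the top level had in practice, and report severity and seriousness separately where source records allow.

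The cost is two revised sentences and at most one form field, or no new field if the questionnaires or case-report form already hold both items. Any retrospective separation adds a review of source records, the size of which cannot be judged from the documents.

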### **Exclusion Criteria:**

- 1) inability to provide informed consent, or for individuals with a legal guardian, inability to provide assent or a lack of informed consent from the legal guardian
- 2) current substance abuse
- 3) Subjects who are not on a stable dose of an antipsychotic medication for at least a month prior to enrollment
- 4) psychiatrically unstable per treating clinician's judgment
- 5) Uncontrolled medical condition including uncontrolled hypertension, diabetes, seizure disorder, severe cardiovascular, cerebrovascular, pulmonary, thyroid diseases, and gastroparesis.
- 6) history of ketoacidosis
- 7) currently taking insulin
- 8) currently taking meglitinides (repaglinide and nateglinide)

- 9) currently on immunosuppressant medication regularly including oral steroids; topical and inhalant steroids are allowed
- 10) currently on sulfonylurea drugs (e.g. glyburide)
- 11) Current, active chronic infection (including tuberculosis, HIV and hepatitis), malignancy, organ transplantation, blood dyscrasia, central nervous system demyelinating disorder, and any other known autoimmune or inflammatory condition
- 12) pregnant or breastfeeding.
- 13) prisoners
- 14) Exclusionary labs: eGFR < 35 ml/min

Hematology (CBC)	
Leukocytes	<2 or $>17.5 \times 10^3/\text{mm}^3$
Platelets	<75 or $>700 \times 10^3/\text{mm}^3$
Comprehensive Metabolic Panel	
Sodium	<1.1 times the lower limit ( $\leq 121.5$ ) or $>1.1$ times upper limit ( $\geq 159.5$ ) of the reference range
Potassium	<1.1 times the lower limit ( $\leq 3.15$ ) or $>1.1$ times upper limit ( $\geq 5.83$ ) of the reference range
Glucose	$>2$ times the upper limit ( $>198$ ) of the reference range
Blood Urea Nitrogen (BUN)	$>1.3$ times upper limit ( $>29.9$ ) of the reference range
Creatinine	$>1.3$ times upper limit ( $>1.69$ ) of the reference range
Total bilirubin	$>2$ times the upper limit ( $>2.4$ ) of the reference range
Aspartate amino transferase (AST)	$>3$ times upper limit ( $>120$ ) of the reference range
Alanine amino transferase (ALT)	$>3$ times upper limit ( $>120$ ) of the reference range
Alkaline phosphatase (ALP)	$>3$ times upper limit ( $>345$ ) of the reference range
Hemoglobin A1C	Patients with a value $\geq 9.0\%$

All exclusionary labs will be reviewed prior to administration of the study drug.

We will continue our recruitment efforts to assure a meaningful representation of women and minority populations.

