Screening visit: Fasting blood samples for glucose, insulin, HbA1c, lipid profile, comprehensive metabolic profile, CBC, high sensitivity CRP, eGFR and TNF- $\alpha$  will be obtained at the screening visit. Subjects will not receive study medication until all baseline labs have been completed, reviewed, and determined to fall within range. Potential subjects will undergo a diagnostic evaluation. Psychiatric diagnosis will be determined using the Structured Clinical Interview for DSM-IV Axis I Disorders (SCID). A medical evaluation, including weight, height, vital signs (heart rate, sitting, and standing blood pressures), a physical examination, and review of systems will be performed. The screening process includes a comprehensive review of medical history & evaluations, which is then reviewed by the PI before continuing with randomization. The study doctor discusses the patient's medical history with the patient, completes a review of systems, a physical exam, assesses the patient's overall health status, and reviews all available medical records, previous laboratory assessments and other relevant medical information in addition to the patient's self-report. Based on all of the information gathered, the PI then assesses the patient's eligibility for the study utilizing their clinical judgment. A urine pregnancy test will be performed on women of childbearing potential. Weekly reminders will be provided to the subject to use condoms or other appropriate birth control. The subjects will be given an appointment card for their next visit which will also provide a reminder for the use of appropriate birth control. In addition, a urine drug screening, and a 12-lead EKG will be performed. The screening visit will take about 2 hours. While the study team plans to complete all assessments in one study visit, it is likely that due to symptoms of psychosis, including avolition, apathy and cognitive disturbances subject may have inconsistent behavior and variable tolerance to screening procedures and assessment batteries. In such cases the subject may be called for an additional visit to complete the remaining procedures or they will be completed in the following visit. Following the screening visit, the subjects' primary care provider and/or psychiatrist will be notified of their participation in the study in order to adequately screen subjects, ensure that only eligible subjects are enrolled, and minimize subject risk. Ongoing subjects will be re-consented and informed of this notification during that time.

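### A first on-study eGFR below 30 means termination under Section 13 but a repeat test under Section 14, and nothing holds the weekly injection while a low value is repeated

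*Protocol*

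**What the plan says.** **Renal limits.** The exclusion criteria in Section 5 of the protocol give the entry limit: "Exclusionary labs: eGFR < 35 ml/min". Section 13 sets an on-study limit: "Subjects will be terminated from the study if their eGFR falls below 30 ml/min at any point during the study". It mentions no repeat test. Section 14 withdraws anyone found to meet an ineligibility criterion after enrolment, and adds: "If subjects have laboratory results that meet the exclusionary criteria range during the study, the subject will have his/her labs repeated before being withdrawn". That sentence covers every exclusionary laboratory value, so it brings the eGFR limit of 35 into the treatment period.

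**Holding the drug.** Section 10 withholds the first dose: "Subjects will not receive study medication until all baseline labs have been completed, reviewed, and determined to fall within range". It also withholds the next dose when a visit with a scheduled blood draw is missed, until the late draw has been taken and signed off. Neither provision concerns a result that is available and out of range during treatment.

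**Psychiatric limit.** Section 13 introduces the PANSS rule with these words: "An explicit stopping rule will be followed for a potentially serious psychiatric decompensation in order to further enhance patient safety". The rule itself, measured against the baseline score, is that "active subjects will be terminated from the study if they experience an increase in PANSS total score greater than or equal to 20". Section 14 says that study medication stops for a serious adverse event, "but will not necessarily be stopped for exacerbation of psychiatric symptoms or any other adverse event". If an investigator considers continuation safe and the subject wishes it, the treating psychiatrist "will be contacted and will make the final decision whether the subject will be allowed to continue taking study medication".

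**The concern.** These are the rules that take an individual subject off drug, so staff should be able to apply them in only one way. Two coordinators who both follow the protocol could handle a first eGFR below 30 differently: one ends participation under Section 13, and the other orders a repeat under Section 14.

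The second issue is what happens to dosing meanwhile. Injections are weekly. The protocol stops dosing when a laboratory result is missing, but it has no matching instruction when the result is present and abnormal. Section 14 can therefore be followed to the letter while a subject with an unresolved low eGFR receives a further dose. Section 15 lists renal impairment and acute renal failure among the postmarketing reports for exenatide, so this is a risk that the protocol itself names.

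**Working it through.** The plan gives no figure on this point, so there is none to reproduce. The power statement in Section 12 does not enter the check.

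**Inputs, all from the protocol**
- Entry limit: eGFR below 35 ml/min (Section 5).
- On-study termination: eGFR below 30 (Section 13).
- Repeat before withdrawal for any exclusionary laboratory value (Section 14).
- Injections at baseline and weekly at weeks 1 to 23 (Section 10).
- On-treatment eGFR draws at weeks 6, 12, 18 and 24 (Section 10).
- Redraw after a failed draw: one week (Section 10). This is the only redraw interval given. None is given for an abnormal value.

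**Step 1. What each section requires**

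| First on-study eGFR (ml/min) | Section 13 | Section 14 | Next injection |
|---|---|---|---|
| 35 or above | no action | no action | given |
| 30 to below 35 | no action | repeat, then withdraw if confirmed | no instruction to hold |
| below 30 | terminate; no repeat mentioned | repeat before withdrawal | none under Section 13; no instruction to hold under Section 14 |

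In the middle row the sections do not conflict, because Section 14 acts and Section 13 is silent. In the bottom row they give different actions for the same value.

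**Step 2. When the bottom-row difference matters**
- If the repeat is below 35, the subject leaves under either section. The difference is timing, and any injection given in between.
- If the repeat is 35 or above, Section 13 has already ended participation, while Section 14 would keep the subject. This takes Section 14's repeat in its natural sense, as a check whose result decides.

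The missing hold affects the middle row on either reading, and the bottom row as well if Section 14 is followed.

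**Step 3. Doses at issue**
- Planned injections: 1 + 23 = 24.
- On-treatment draws followed by further weekly injections: weeks 6, 12 and 18, so 3 of 4.
- Assumptions: the first result is known before the next weekly visit, and the repeat is drawn one week after the first draw (week 7, 13 or 19).
- The injection due at that visit falls before the repeat result: 1 injection, 1/24 = 4.2%.
- If the repeat result is reviewed more than a week later, the following injection also falls due: 2 injections, 2/24 = 8.3%.
- If the repeat is drawn and reviewed before the next visit, or dosing is held: 0.

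The range is therefore 0 to 2 injections per affected subject. It comes from the dosing calendar and does not estimate how often a low eGFR occurs.

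**The case against.** **The eGFR limits form a workable two-tier rule.** The strongest reply is that Section 13 is the specific rule for values below 30 and Section 14 the general rule for the rest. Much of this stands. A reader might infer that the fate of a confirmed value from 30 to below 35 is left open, or that 30 replaces 35 once a subject is on study. The documents support neither reading: Section 14 withdraws such a subject, and no sentence keeps them in. What does not stand is that the two tiers are stated. Section 14's repeat applies to every exclusionary value, including those below 30, and nothing gives Section 13 precedence.

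**Other safeguards cover the interval.** Drug stops for a serious adverse event (Section 14), potentially serious events go to an external team and the principal investigator monitors laboratory results continuously (Section 13), and the investigators must terminate a subject whose health is compromised by treatment (Section 22). These make harm less likely. But the first two depend on an event being judged serious or potentially so, which a low eGFR on a routine draw may not be, and the others depend on judgement. Section 14's own wording also lets drug continue through adverse events that are not serious.

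**The PANSS rule.** A reader might infer that Section 14 lets the treating psychiatrist override the 20-point limit. The documents do not support that. Section 13 is mandatory and applies at any point. Section 14 says only that drug need not always be stopped for worsening, which fits with a fixed ceiling. It also requires an investigator to consider continuation safe first, and the protocol describes no dosing for a subject already terminated.

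**Section 20.** Its provision for continuing after a treating clinician raises a laboratory result might look like a way round the eGFR limit. It requires the principal investigator's agreement, claims no precedence over Section 13, and is followed by a statement that results can lead to termination.

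**Conclusion.** The concern holds for eGFR and is limited to two defects: conflicting instructions for a first on-study value below 30, and no automatic hold on the weekly injection while a value below 35 is repeated. The size is one injection per affected subject if the repeat takes a week, two if its result is reviewed more than a week later, and none if the repeat is resolved before the next visit. The one-week interval is borrowed from the protocol's provision for failed draws and is an assumption. No rate of low eGFR is given, so no number of subjects follows. No effect on sample size, power or the primary analysis is claimed.

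The PANSS rule and Section 14 can be read together. A cross-reference would help staff, but that is a clarification and does not resolve a contradiction.

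**What to change.** State one eGFR rule, in the same words, in Sections 13 and 14:
- For any on-study eGFR below 35 ml/min, hold the weekly injection until a prompt repeat has been reviewed by the principal investigator.
- Withdraw the subject if the repeat confirms a value below 35, as Section 14 already provides.
- Terminate at a value below 30 without waiting for a repeat, as Section 13 already provides.

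As a minor clarification, add to Section 14 that the treating psychiatrist's discretion applies to PANSS total rises below 20 points from baseline, and that Section 13 governs at 20 or more.

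The cost is a few sentences. No scheduled visits or assessments are added and the sample size does not change. For an affected subject, about 1 to 2 of 24 injections would be delayed, on the same one-week assumption. Terminating on a single value below 30 means that a spurious result would end participation, but Section 13 as written already accepts that.
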